### 10.2.3 Outcome Categorization

Outcome may be classified as recovered without sequelae; recovered with sequelae; improved; worsened; ongoing; ongoing at end of study; fatal; or unknown. If the outcome is reported as recovered with sequelae for an SAE, the Investigator should specify the kind of sequelae on the SAE reporting form. SAEs that are ongoing at the time of death will have an outcome of “unknown” recorded. SAEs resulting in a fatal outcome will have an outcome of “fatal” recorded.

#### **10.2.4 Symptoms of the Disease Under Study**

Symptoms of the disease under study will not be classed as AEs as long as they are within the normal day-to-day fluctuation of the disease. An explanation of these circumstances must be written in the source documents.

Worsening of the symptoms however, will be recorded as an AE, and clearly marked as worsening or by the subject's worst observed intensity.

#### **10.2.5 Clinical Laboratory Evaluations**

A change in the value of a safety laboratory investigation can represent an AE if the change is clinically relevant in the opinion of the Investigator or if, during treatment with the study treatment, a shift of a parameter is observed from a normal value to a pathological value, or a further worsening of an already pathological value.

If, at the end of the treatment phase, there are pathological laboratory values which were not present at baseline, further clinical or laboratory investigations will be performed until the values return to within reference range or until a plausible explanation (e.g., concomitant disease) is found for the pathological laboratory values.

If the Investigator considers such an AE as serious it must be reported as an SAE.

#### **10.2.6 Abuse, Misuse, Overdose and Medication Error**

All AEs of special interest such as study treatment abuse, misuse, overdose, and medication error have to be documented in the subject's eCRF and source documentation. If any occurrence of abuse, misuse, overdose, or medication errors leads to any event that fulfils any seriousness criteria, the event has to be reported as an SAE.

### **10.3 Reporting Procedure for AEs, SAEs, and Pregnancy**

#### **10.3.1 Adverse Events**

All AEs either observed by the Investigator or one of his/her medical collaborators, or reported by the subject spontaneously, or in response to a direct question, will be noted in the AE section of the subject's eCRF and source documentation. This applies to all AEs regardless of presumed relationship to the study treatment. Adverse events leading to discontinuation of study treatment must be collected.

If any AE is reported, the date of onset, relationship to study treatment, any action taken, date of resolution (or the fact that it is still continuing or has become chronic), outcome, and whether the AE is serious or not, will be recorded. Use of colloquialisms and abbreviations should be avoided. Only 1 AE term should be recorded in the event field on the AE eCRF. Where possible, the Investigator should report a diagnosis rather than signs and symptoms or

abnormal laboratory values. However, if a constellation of signs and/or symptoms cannot be medically characterized as a single diagnosis or syndrome at the time of reporting, each individual event should be recorded on the AE eCRF. If a diagnosis is subsequently established, all previously reported AEs based on signs and symptoms should be nullified and replaced by one AE report based on the single diagnosis, with a starting date that corresponds to the starting date of the first symptom of the eventual diagnosis.

The AE reporting period begins at the time the ICF is signed by the subject. The AE reporting period ends at Visit 15 (if the subject participates in the continuation study) or the study follow-up visit (Visit 16), if the subject does not participate in the continuation study. Adverse events persisting at the time of study completion will be followed by the Investigator through contact with the subject until resolution or stabilization has occurred (or the subject is lost to follow-up and cannot be contacted) and recorded in the source documents. If the subject reports an AE, it is the Investigator's responsibility to acquire sufficient information in order to assess causality. This may require additional laboratory testing, physical examinations, telephone contacts, etc. In circumstances where the Investigator is unable to make contact with the subject, the Investigator must provide a written statement to Aurinia confirming that the subject is lost to follow-up.

In order to avoid bias in eliciting AEs, subjects should be asked a non-leading question, such as "How are you feeling?" It is also important to question the subject in a non-leading way about changes in their health or concomitant medication usage since their last visit. This information should be collected prior to completion of assessments at all study visits. In addition, any symptoms/conditions reported during assessments and deemed to be clinically significant by the Investigator will be considered AEs.

### **10.3.2 Serious Adverse Events**

All SAEs occurring after the signing of the ICF will be reported to [REDACTED] within 24 hours of the Investigator, designee, or site staff's knowledge of the event regardless of relationship to study treatment. All SAEs are to be reported on the eCRFs.

In the event that the site experiences a temporary disruption of the EDC system a back-up paper SAE Reporting Form will be available for site staff to complete.

- Site staff will complete the paper SAE report form and e-mail it within 24 hours to the following address: [REDACTED]
- Only in cases where the email system is unavailable, site staff will send the SAE by fax to: [REDACTED] (US) and [REDACTED] (Outside US).

If notification is made via email or fax, site staff must enter the SAE information into the electronic data capture (EDC) system as soon as the system becomes available.

All SAEs, regardless of causality, will be reported from the time the ICF is signed until 30 days following the last study visit or 30 days after last study treatment administration in subjects who withdraw or discontinue prior to study completion. No formal study visit is required but Investigators must report any SAEs that occur during this 30 day period on the eCRF. If the Investigator has not seen the subject at a clinic visit at the end of the reporting period, the Investigator must make reasonable efforts to contact the subject to inquire about SAEs.

All recorded SAEs, regardless of relationship to study treatment, will be followed up until resolution, stabilization, or the subject is lost to follow-up and cannot be contacted. In circumstances where the Investigator is unable to make contact with the subject, the Investigator must provide a written statement to Aurinia confirming that the subject is lost to follow-up.

Any SAE considered to have a causal relationship (i.e., “related”) to the study treatment and discovered by the Investigator at any time after the study will be reported. A rationale for the assessment of a causal relationship must be provided by the Investigator. Any safety information that is obtained after the Follow-up Visit (Visit 16) will be documented in the safety database only.

A death occurring during the study or which comes to the attention of the Investigator within 30 days after the last study visit (including the Follow-up Visit) or until 30 days after the last study treatment administration, whichever is longer, whether considered treatment-related or not, must be reported to Aurinia. If the subject died, the SAE report should include the cause of death as the event term and whether or not the death was related to study treatment, as well as the autopsy findings, if available. Preliminary reports will be followed by detailed descriptions which will include copies of hospital case reports, autopsy reports/certificates and other documents when requested and applicable.

Additional follow-up information must be reported in the eCRF within 24 hours of awareness following Investigator (or site) awareness of the information. The Investigator should not delay reporting an SAE in order to obtain additional information. Additional information, when available, should be reported to [REDACTED] by the reporting procedures described above.

The Investigator is encouraged to discuss with the study Medical Monitor when the issue of seriousness is unclear or questionable.

An investigator who receives an investigator safety report describing an SAE or other specific safety information (e.g., summary or listing of SAE) from the sponsor will file it along with the IB and will notify the IRB/IEC, if appropriate according to local requirements.

The sponsor or its representative will be responsible for determining and, in turn, reporting SAEs to regulatory authorities according to the applicable regulatory requirements.

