Procedures:	
See Schedule of Events for full details of protocol required procedures and applicable visits (and timings). Subjects who have provided signed and dated informed consent will be screened for entry into this study. Baseline proteinuria level is determined by a mean of 2 first morning void urine samples taken during the screening period. If a subject has not had a kidney biopsy within the required timeframe for study eligibility, one may be performed to assess eligibility into the study, provided consent is in place and provided the results are received before randomization. Subjects meeting the required eligibility criteria will be randomized in a ratio of 1:1 to receive either Orelvo (23.7 mg BID) or matching placebo starting on Day 1. All subjects will receive initial treatment with 0.5 to 1.0 g IV methylprednisolone. In consultation with the Medical Monitor, and if it is in the subject's best interest, IV methylprednisolone may be started during the screening period. Subjects receiving IV methylprednisolone in the 3 months prior to screening must be discussed with the Medical Monitor prior to initiating further IV methylprednisolone. For subjects who are not already taking prescribed MMF prior to randomization, the dosing of MMF will start at 500 mg BID for a total daily dose of 1 g/day for the first week, increasing to 1 g BID for a total daily dose of 2 g/day for the second and subsequent weeks (i.e., beginning on Day 8).
 
All subjects will complete dosing through 52 weeks of study treatment. Subjects who permanently discontinue study treatment before the Week 52 visit will return for all remaining study visits and assessments unless they have withdrawn consent. All subjects who complete participation and study treatment through 52 weeks and provide consent will have the opportunity to enroll into a continuation study for which the details are not yet finalized.

Sample Size:	
A 2 group continuity corrected Chi square test with a 0.05 two-sided significance level will have 80% power to detect the difference between a placebo response rate of 20.0% and an Orelvo response rate of 34.4% (odds ratio=2.1) when the sample size in each group is 162 (total N=324). While the effect of withdrawals will be investigated, subjects withdrawing for any reason will be counted as non-responders in the primary analysis and therefore no adjustment of sample size for withdrawals is necessary.

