### **9.2.4 Follow-up Procedures**

All subjects who complete the study but do not participate in the continuation study or discontinue study treatment before Week 52 will be followed up 4 weeks ( $\pm 10$  days) after their last study treatment dose to collect any new AEs and concomitant medications. This visit (Visit 16) will be conducted as an in-clinic visit.

Assessments for the follow-up visit are as follows:

- Vital signs
- Blood sample collection for analysis at central laboratory (eGFR)
- First morning void urine sample collection
- Concomitant medication
- AEs
- Confirmation of completed follow-up visit using IWRS

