### **13.9 Safety Evaluations**

Specific safety endpoints are as follows:

- Biochemical (including liver function tests) and hematological laboratory tests
- AE profile and routine biochemical and hematological safety parameters
- Vital signs (BP, HR, temperature) at specific time points and change from baseline
- Standard 12-lead ECGs change from baseline
- Discontinuations from treatment
- Concomitant medications

Laboratory values, vital signs, and other safety parameters providing numeric data will be summarized by treatment arm, visit, and as change from baseline.

Adverse events will be coded using the latest available version of the Medical Dictionary for Regulatory Activities, the version of which will be provided in the clinical study report.

Treatment-emergent adverse events will be summarized by treatment arm, system organ class, and preferred term. SAEs, SAEs that led to death, and SAEs/AEs that led to withdrawal will also be summarized and listed.

Only AEs which started on or after the date of first dose of study treatment will be considered TEAEs, though all AEs after informed consent will be recorded. SAEs occurring at any time after informed consent will be summarized. All concomitant medications will be summarized.

Details of these and other analyses will be provided in the SAP.

All study data analyses involving laboratory values will be based on results from the central laboratory.

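### Read literally, Protocol 10.3.2 closes SAE reporting for early stoppers 30 days after last dose while their study visits continue

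*Protocol*

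**What the plan says.** **SAE period (Protocol 10.3.2).** The section opens with an unlimited rule: "All SAEs occurring after the signing of the ICF will be reported to" a named recipient within 24 hours. A later paragraph defines the period. SAEs of any causality are reported "from the time the ICF is signed until 30 days following the last study visit", or, as the alternative end point, "30 days after last study treatment administration in subjects who withdraw or discontinue prior to study completion". Nothing says which end point governs a subject who is off drug but still attending. For deaths, the same section uses the longer of last visit plus 30 days and last dose plus 30 days ("until 30 days after the last study treatment administration, whichever is longer"), and 10.3.3 does the same for pregnancies. Related SAEs that come to light after the study stay reportable without limit.

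**Visits after stopping drug.** The synopsis states: "Subjects who permanently discontinue study treatment before the Week 52 visit will return for all remaining study visits and assessments", unless consent is withdrawn. The notes to the Schedule of Events, Section 5.6 (where possible) and Section 9.1.4.1 agree.

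**AE period (Protocol 10.3.1).** It closes at Visit 15 for subjects entering the continuation study and at Visit 16 for the rest. Section 9.2.4 says that subjects who "discontinue study treatment before Week 52 will be followed up 4 weeks" after their last dose, at Visit 16. The Schedule column and Section 4.1 put Visit 16 at Week 56.

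**Analysis.** Protocol 13.9 promises: "SAEs occurring at any time after informed consent will be summarized". SAP 6.13.1 limits TEAEs to onset no later than 30 days after last dose. SAP 6.13.1.1 counts time at risk to the end of the study for subjects without the event.

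**The concern.** The protocol keeps treatment stoppers on visits for good reason: they are counted in the ITT analysis and remain under observation. The SAE limb that on its face applies to them is tied to the last dose, not the last visit. A site that applies the specific rule could stop sending 24-hour reports for non-fatal SAEs judged unrelated, in a subject it still sees every few weeks. Another site, relying on the opening sentence or the Schedule, would go on reporting.

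At stake is uniform SAE ascertainment off treatment. After a stop for non-response, Section 5.6.1 leaves further therapy to the investigator. If sites differ in what they report, the summary promised in 13.9 rests on uneven collection.

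**Working it through.** The plan gives no figure to reproduce here. The check is date arithmetic plus a comparison of passages.

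**Inputs.** The limb ends 30 days after last dose (10.3.2). Visits run to Week 52, nominally day 364 (synopsis, Schedule). The stopping week is an assumption, shown as a range. Week 8 is the earliest point named in the non-response criteria of 5.6.1, although stops for adverse events can come sooner.

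**Formula (literal reading).** For last dose on day d = 7 × week, days outside the limb = max(0, 364 − (d + 30)).

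| Stop | Limb closes (day) | Days outside | Share of time after last dose | Share of 364 days |
|---|---|---|---|---|
| Week 8 | 56 + 30 = 86 | 278 | 278/308 = 90% | 76% |
| Week 12 | 84 + 30 = 114 | 250 | 250/280 = 89% | 69% |
| Week 24 | 168 + 30 = 198 | 166 | 166/196 = 85% | 46% |
| Week 36 | 252 + 30 = 282 | 82 | 82/112 = 73% | 23% |
| Week 42 | 294 + 30 = 324 | 40 | 40/70 = 57% | 11% |
| Week 48 | 336 + 30 = 366 | 0 | 0% | 0% |

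After a Week 8 stop, eight scheduled visits lie beyond day 86 (Weeks 16, 20, 24, 30, 36, 42, 48 and 52).

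**When is more than half outside?** Of the time after last dose: 334 − d > (364 − d)/2, so d < 304, about Week 43. Of the whole 52 weeks: 334 − d > 182, so d < 152, about Week 22.

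**Narrow reading (the limb covers only subjects who leave the study).** A subject stops drug at Week 8, attends to Week 40 (day 280) and then withdraws. This subject has withdrawn before completion, so the limb applies. Days outside = 280 − 86 = 194, about 28 weeks of attended follow-up. A subject who stops drug and stays to Week 52 has no gap on this reading.

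**Trial-wide scale (literal reading, assumed rates).** The documents give no expected discontinuation rate. If 10% to 20% of 324 subjects stopped at Week 24 on average and stayed to Week 52, that is 32.4 to 64.8 subjects. Multiplied by 166/364, this gives about 15 to 30 subject-years.

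**AE period.** If Visit 16 follows 9.2.4, a Week 8 stopper has it at about Week 12, and the 10.3.1 period ends there although the Schedule collects AEs at every later visit. If Visit 16 is at Week 56, the AE period covers all visits. The timing also matters because 10.3.2 sends safety information obtained after Visit 16 to the safety database only.

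**SAP.** An event-free Week 8 stopper who stays to Week 52 contributes 364 days at risk (taking Week 52 as end of study), but only the first 86 can yield a TEAE. The other 278 enter the denominator of the exposure-adjusted rate with no possible event.

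**After the fix.** With the later-of-two-dates rule, the attended days left uncovered are 0 at every stopping time.

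**The case against.** The best defence is that the limb is about leaving the study. It does not name study treatment as the thing discontinued, whereas the synopsis, 5.6 and 9.2.4 do when they mean drug only. The sentences after it say that no formal visit is needed and ask the investigator to try to contact a subject not seen in clinic, which fits people who no longer attend. On that view a subject who stops drug but stays to Week 52 completes the study and is covered to last visit plus 30 days. This is a fair reading, but not the only one. The protocol often uses discontinuation for treatment and withdrawal for the study, the limb is anchored on last dose, and if both verbs meant leaving the study the second would add little. The narrow reading also leaves the stop-then-withdraw case open.

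The second defence is that much remains reportable. The opening sentence of 10.3.2 has no end date, 10.3.1 records seriousness for every AE, AEs are elicited at all visits, deaths have the longer window, and related SAEs have no limit. Section 13.9 also says that AEs after consent will be recorded. This largely stands. The exposure is mainly the 24-hour route for non-fatal SAEs judged unrelated.

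A reader might infer three stronger things, none of which the documents support:
- That these SAEs are outside mandatory reporting, or lost. The rules just listed point the other way.
- That they would not reach the DSMB. Section 12 supplies it with eCRF tables and listings, including AE and SAE data, and does not tie these to 24-hour reports.
- That voclosporin would lose more. In Phase 2, SAEs were 25.8% on low dose against 15.8% on placebo, and discontinuations for decreased GFR 6.7% against 1.1%. SAE rates are not discontinuation rates, and decreased GFR is one reason among several. Stops for non-response could run the other way, and overall discontinuation by arm is not given.

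**Conclusion.** The point holds as a conflict between stated rules. On its literal terms, 10.3.2 leaves non-fatal SAEs outside the defined window for 278 attended days after a Week 8 stop, 166 after a Week 24 stop and none after a Week 48 stop, assuming attendance to Week 52. On the narrow reading the gap shrinks to subjects who stop drug and later withdraw, about 28 weeks in the worked example. To say that most follow-up is affected is true of time after last dose only for stops before about Week 43, and of the full 52 weeks only before about Week 22. The 15 to 30 subject-years rest on assumed rates and the literal reading. Capture depends on site interpretation; neither loss from the database nor imbalance between arms is established. The timing of Visit 16 and the mismatch between the SAP's TEAE window and its time at risk are related and should be settled together. The change should be made, because it removes a conflict with 13.9 using a rule that the protocol already applies elsewhere.

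**What to change.** - **Protocol 10.3.2:** for all subjects, end SAE reporting 30 days after the last study visit or 30 days after the last study treatment administration, whichever is later.
- **Protocol 10.3.1, 9.2.4 and Schedule:** end the AE period at the later of Visit 16 and the subject's last study visit, and state one timing for Visit 16 in subjects who stop drug but stay in the study.
- **SAP 6.13.1:** summarize all SAEs after consent, as 13.9 promises, with those starting more than 30 days after last dose shown separately. The body of 6.13.1 names serious-TEAE summaries; the contents of the Section 11 table list are not in the text available, so check whether such a table is already there.
- **SAP 6.13.1.1:** make time at risk and the event window end on the same date.

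The cost is a short protocol amendment, site notification, a small SAP edit and a few more SAE reports from subjects who are already attending. No visits are added.

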### **10.3.3 Pregnancy**

Pregnancy occurring in a female subject or in the partner of a male subject should be reported to [REDACTED] within 24 hours of becoming aware of the event using the pregnancy eCRF. The Investigator should counsel the subject, and in the case of a male subject, the subject's partner, discuss the risks of continuing with the pregnancy and the possible effects on the fetus. A female subject must immediately inform the Investigator if she becomes pregnant during the study. Monitoring of the pregnancy in a female subject should continue until conclusion of the pregnancy. In case of a pregnancy in the partner of a male subject, the Investigator should obtain informed consent of the pregnant partner prior to monitoring of the pregnancy.

Women who have a positive pregnancy test during the study will be withdrawn from the study treatment and the procedures for withdrawal will be completed. The Medical Monitor must be contacted immediately to break the blind (if applicable).

All pregnancies, subject or partner of a subject, that occur during the study or come to the attention of the Investigator within 30 days after the last study visit (including the Follow-up Visit) or until 30 days after last study treatment administration, whichever is longer, must be reported to [REDACTED] by the reporting procedures described above.

The outcome of all such pregnancies (including normal births) should be followed up and documented, even if the subject was withdrawn from the study. Every effort should be made to gather information regarding the pregnancy outcome until 90 days (or otherwise as appropriate) post-partum. It will be the responsibility of Aurinia, together with the appropriate support of the Investigator, to obtain this information.

Complications of pregnancy such as abortion (spontaneous or induced), premature birth, or congenital abnormality are considered SAEs and should be reported following the reporting procedures as outlined in Section [10.3.2, Serious Adverse Events](#). In the event that the site experiences a temporary disruption of the EDC system, a back-up paper Pregnancy Reporting Form will be available for site staff to complete.

